7.3 Protocol Deviations

Protocol deviations include eligibility criteria violations, receipt of wrong treatment or incorrect dose of study treatment, development of withdrawal criteria without being withdrawn, and use of prohibited concomitant medications.

For each of the following protocol deviation categories and across all categories, the number and percentage of randomized subjects with at least one protocol deviation will be summarized overall and by treatment group:

- Subject entered into the study even though s/he did not satisfy entry criteria;
- Subject developed withdrawal criteria during the study but was not withdrawn;

- Subject received wrong treatment or incorrect dose of study treatment;
- Subject took prohibited concomitant medication.

8.0 Handling of Potential Intercurrent Events for the Primary and Key Secondary Endpoints

The efficacy endpoints (defined in Section 3.1, Section 3.2, and Section 3.3) will be analyzed based on the ITT populations. No intercurrent events will be considered in this study.

9.0 Efficacy Analyses

9.1 General Considerations

All efficacy analyses will be conducted on the ITT Population separately for each study.

The primary analysis will be performed when all ongoing subjects complete Week 16 of Study-G and Study-S and all data pertaining to Period A are cleaned. The Week 16 analysis is the only and final analysis for efficacy in Period A.

The final analysis will be conducted upon study completion.

For categorical variables, the number and proportion of subjects, and the 95% confidence interval (CI) of the proportion will be provided by each treatment group among ITT Populations.

In addition, comparisons between RZB and placebo will be analyzed using the Cochran-Mantel-Haenszel (CMH) test adjusting for the actual values of stratification factors weight (≤ 100 kg, > 100 kg) and number of prior biologic therapies for psoriasis ($0, \geq 1$), with a 2-sided significance level of 0.05 for each study. The CMH test will use weights proposed by Greenland & Robins, which is calculated as follows:

$$\hat{\delta}_{MH} = \frac{\sum_{i=1}^4 w_i \hat{\delta}_i}{\sum_{i=1}^4 w_i}, \text{ where}$$

- $\hat{\delta}_i = \frac{x_i}{n_i} - \frac{y_i}{m_i}$ denotes the risk difference in stratum $i, i = 1, \dots, 4$.
- $w_i = \frac{n_i m_i}{n_i + m_i}$ denotes the weight of stratum $i, i = 1, \dots, 4$.
- x_i denotes the number of subjects with event in RZB in stratum $i, i = 1, \dots, 4$.
- y_i denotes the number of subjects with event in PBO in stratum $i, i = 1, \dots, 4$.
- n_i denotes the number of subjects in RZB in stratum $i, i = 1, \dots, 4$.
- m_i denotes the number of subjects in PBO in stratum $i, i = 1, \dots, 4$.

The estimated variance of $\hat{\delta}_{MH}$ is calculated as:

$$\widehat{var}(\hat{\delta}_{MH}) = \frac{\sum_{i=1}^4 L_i}{(\sum_{i=1}^4 w_i)^2}$$

$$\text{where } L_i = \frac{x_i(n_i - x_i) m_i^3 + y_i(m_i - y_i) n_i^3}{n_i \cdot m_i \cdot (n_i + m_i)^2}, i = 1, \dots, 4$$

Assuming a normal distribution of $\hat{\delta}_{MH}$, an approximate 95% CI is given as follows, where $z_{0.975}$ is the 97.5% quantile of $N(0, 1)$:

$$CI = \left[\hat{\delta}_{MH} \pm z_{0.975} \cdot \sqrt{\widehat{var}(\hat{\delta}_{MH})} \right]$$

The approximate p-value can be calculated using the following:

$$p - \text{value} = 2 \cdot \Pr \left[Z > \left| \frac{\hat{\delta}_{MH}}{\sqrt{\widehat{var}(\hat{\delta}_{MH})}} \right| \right], \text{ where } Z \sim N(0, 1)$$

If there is a stratum with zero subjects in either treatment group, the 0 count will be replaced by 0.1 in order to prevent dividing by 0 in the above equations, as suggested in Greenland & Robins. In case of any stratum with zero subjects in both treatment groups, the corresponding stratification factor will not be controlled.

For continuous variables, the Baseline mean, visit mean, as well as the Least Square (LS) mean, 95% confidence interval (CI) and Standard Error (SE) of the mean, will be reported for each ITT Population. The comparisons between RZB and placebo will be analyzed using Mixed-Effect Model Repeated Measurement (MMRM) method, adjusting for the fixed effects of treatment, actual values of stratification factors at Baseline, Baseline value, visit and treatment by visit interaction as covariates.

"Baseline" refers to the last non-missing observation on or before the date of the first administration of study drug, or the date of randomization if no study drug is administered.

For analyses by stratification factors used for randomization, any subject who is randomized within an incorrect stratum will be analyzed according to the actual stratum to which the subject belongs.

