7.4 Statistical Analyses for Efficacy

Summary and Analysis of the Primary Endpoint

Analysis of the primary endpoint will be conducted on the ITT_G and ITT_S Populations for Study-G and Study-S, respectively, based on treatment as randomized.

Comparison of the primary endpoint will be made between risankizumab and placebo using the CMH test adjusting for the actual values of stratification factors weight (≤ 100 kg vs. > 100 kg) and number of prior biologic therapies for psoriasis (0 vs. ≥ 1), with a 2-sided significance level of 0.05 for each study.

Handling of Missing Data

- Non-responder Imputation (NRI) will be the primary approach to handle missing values. In cases data missing at random can be reasonably assumed, NRI while incorporating multiple imputation to handle any missing data that can be reasonably assumed to be Missing at Random (NRI-MI) will be used.

Details for NRI, NRI-MI, and other sensitivity analysis (if applicable) will be provided in the SAP.

Summary and Analysis of Ranked Secondary Endpoints

Analysis of all ranked secondary efficacy endpoints will be conducted on the ITT_G and ITT_S Populations based on treatment as randomized respectively in each study.

The categorical endpoints will be analyzed using the CMH test described above.

The continuous endpoints will be analyzed using a MMRM, including baseline, adjusting for treatment, actual values of stratification factors, visit, and treatment by visit interaction.

Summary and Analysis of Additional Efficacy Endpoints

Details for the analyses of additional efficacy endpoints will be provided in the SAP.

Subgroup Analysis for Efficacy

To evaluate the consistency of the efficacy across demographic and other baseline characteristics, the number and percentage of subjects achieving sPGA-G of 0 or 1 at Week 16 (for ITT_G Population) and scalp IGA of 0 or 1 at Week 16 (for ITT_S Population) will be summarized among the following subgroups:

- BMI (normal: < 25; overweight: ≥ 25 to < 30; obese: ≥ 30)
- BSA (< 10%, ≥ 10%)
- Prior biologic therapies for psoriasis (0, ≥ 1)
- Weight (≤ 100 kg, > 100 kg)
- Baseline sPGA (3,4)
- Baseline sPGA-G (3,4) for Study-G only
- Baseline scalp IGA (3,4) for Study-S only
- Baseline PSSI (by median) for Study-S only

The BMI ≥ 30 subgroups will be combined with the adjacent subgroup when having fewer than 10% subjects.

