7.8 Sample Size Determination

This study plans to enroll approximately 100 subjects into Study-G and 100 subjects into Study-S to be sufficiently powered to detect the treatment difference between risankizumab and placebo with respect to the primary endpoints within each study.

- In Study-G, assuming the treatment difference versus placebo (13%) in sPGA-G 0/1 at Week 16 is 53%, a total sample size of N = 100 subjects (risankizumab: 50; placebo: 50) will provide more than 90% power to detect the treatment difference between risankizumab and placebo, using a Chi-square test with a 2-sided significance level of 0.05.
- In Study-S, assuming the treatment difference versus placebo (11%) in Scalp IGA 0/1 at Week 16 is 37%, a total sample size of N = 100 subjects (risankizumab: 50; placebo: 50) will provide more than 90% power to detect the treatment difference between risankizumab and placebo, using a Chi-square test with a 2-sided significance level of 0.05.

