2.3 Treatment Assignment and Blinding

All subjects will be assigned a unique identification number by the interactive response technology (IRT) at the screening visit. For subjects who rescreen, the screening number assigned by the IRT at the initial screening visit should be used. The IRT will assign a randomization number that will encode the subject's treatment group assignment according to the randomization schedule.

Subjects who satisfy eligibility criteria for Study-G only or Study-S only will be assigned to Study-G or Study-S, respectively. Subjects who meet the criteria for both Study-G and Study-S will first be randomized to either Study-G or Study-S with equal probability and then will be randomized to receive either RZB or placebo in a 1:1 ratio. After one of the two studies reaches 40 subjects in the BSA < 10% group, subjects with BSA < 10% who are eligible for both studies will be automatically assigned to the other study until both studies reach 40 subjects in this BSA < 10% group.

Randomization within each study will be in a 1:1 ratio to receive risankizumab or placebo, stratified by weight (≤ 100 kg vs. > 100 kg) and number of prior biologic therapies for psoriasis (0 vs. ≥ 1).

All AbbVie personnel with direct oversight of the conduct and management of the trial (with the exception of AbbVie Clinical Drug Supply Management Team) will remain blinded until the Primary Analysis at Week 16 is available. The investigator, study site personnel, and the subject will remain blinded to each subject's treatment throughout the study. To maintain the blind, the RZB pre-filled syringe (PFS) and matching placebo PFS provided for the study will be identical in appearance. The IRT will provide access to unblinded subject treatment information in the case of a medical emergency.

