9.5 Additional Efficacy Endpoints and Analyses

All additional efficacy endpoints are as defined in Section 3.3.

Analyses of additional efficacy endpoints will be conducted as specified in Section 9.1 by providing descriptive statistics and comparisons as needed.

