13.0 Overall Type-I Error Control

For Study-G and Study-S, overall type-I error will be controlled under a two-sided significance level of 0.05 respectively for each study by testing the primary endpoint,

followed by the ranked secondary endpoints, in a hierarchical order as described in Section 3.1 and Section 3.2.

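### SAP 9.1 names a CMH test but prints an unpooled Wald test, whose two-sided type I error at N=100 is about 6.2–6.6%, not 5%

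*SAP*

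**What the plan says.** Protocol 7.4 states: "Comparison of the primary endpoint will be made between risankizumab and placebo using the CMH test adjusting for the actual values" of the two stratification factors. The ranked categorical secondaries use the same test.

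SAP 9.1 also names the CMH test, "with a 2-sided significance level of 0.05 for each study", and continues: "The CMH test will use weights proposed by Greenland & Robins, which is calculated as follows". It then prints the MH-weighted risk difference, a variance built from terms L_i, a normal-theory 95% CI, and the p-value ("The approximate p-value can be calculated using the following"): twice the upper normal tail beyond |estimate / standard error|. An arm with no subjects in a stratum has its count replaced by 0.1.

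SAP 13.0 promises that "overall type-I error will be controlled under a two-sided significance level of 0.05 respectively for each study", testing the primary and then the ranked secondaries in fixed order. The formula reaches further: "Analyses of additional efficacy endpoints will be conducted as specified in Section 9.1 by providing descriptive statistics and comparisons as needed" (SAP 9.5). The tipping-point analysis in SAP 9.3.3 also takes its p-value from the CMH test. SAP 14.1, which lists departures from the protocol's analyses, does not mention a change of test.

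**The concern.** The CMH chi-square compares observed with expected responders, using the hypergeometric variance that holds when the arms do not differ. The SAP never prints that statistic. The printed one estimates each arm's binomial variance separately within each stratum. With about 100 subjects over eight stratum-by-arm cells, that plug-in variance tends to be too small, so the test rejects too often.

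Each ranked endpoint is tested at the full 0.05, so an excess applies at every binary step. Study-G ranked endpoints 3 and 4 are limited to subjects with a baseline score of at least 4 (genital itch) or at least 2 (GenPs-SFQ item 2), which makes the cells smaller still. The CI uses the same variance, so its coverage is affected too.

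**Working it through.** **Inputs from the documents.** 50 per arm; planned rates 66% v 13% (Study-G: 13% + 53 points) and 48% v 11% (Study-S: 11% + 37 points), from Protocol 7.8 and SAP 2.4; 1:1 allocation within four strata (SAP 2.3); two-sided 0.05.

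**Assumed.** Stratum shares (52.5/22.5/17.5/7.5, four equal quarters, 64/16/16/4, 36/24/24/16%); block size (2 or 4) or no blocking; and 11–13% as the common rate under the null.

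**Plan's own figure.** The two-proportion power formula gives 99.998% (Study-G) and 98.9% (Study-S), so the stated power of more than 90% is correct.

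**Which test is printed.** In stratum i, let x of n respond on risankizumab and y of m on placebo, with w = nm/(n+m). Then

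w²·[x(n−x)/n³ + y(m−y)/m³] = [x(n−x)m³ + y(m−y)n³] / [nm(n+m)²],

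which is the printed L_i. The bracket on the left is the sum of the two arms' separate binomial variances, with no pooling under the null. With t = x+y and N = n+m, the CMH chi-square uses instead

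V = n·m·t·(N−t) / [N²(N−1)].

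**Illustration** (hypothetical counts, one stratum, 11/50 v 4/50):

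- Printed form: difference 0.14; variance 11·39/50³ + 4·46/50³ = 0.003432 + 0.001472 = 0.004904; z = 0.14/0.0700 = 2.00; p = 0.046.
- CMH: observed minus expected 11 − 7.5 = 3.5; V = 50·50·15·85/(100²·99) = 3.220; z = 3.5/1.794 = 1.95; p = 0.051.

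**Exact type I error, 50 v 50 without strata** (full enumeration, 11–13% null): 5.7–5.8% for the unpooled Wald test, 4.8–4.9% for CMH.

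**Stratified type I error** (200,000 null trials per cell, 0.1 rule applied; N=100 except where stated; range over the four mixes):

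| Null rate and design | Printed formula | CMH chi-square |
|---|---|---|
| 11–13%, blocked | 6.2–6.4% | 4.8–5.0% |
| 11–13%, no blocking | 6.4–6.6% | 4.8–5.0% |
| 3% | 3.1–3.7% | 2.6–2.8% |
| 5% | 5.5–5.9% | 4.1–4.6% |
| 8% | 6.3–6.6% | 4.7–5.0% |
| 25% | 6.3–6.5% | 4.9–5.1% |
| Subset N=80, null 10–25% | 6.6–6.8% | 4.7–5.1% |
| Subset N=60, null 10–25% | 7.1–7.7% | 4.5–5.0% |
| Subset N=40, null 10–25% | 8.3–10.0% | 3.6–4.9% |
| Subset N=80, null 5% | 4.9–5.2% | 3.5% |
| Subset N=60, null 5% | 4.5–4.7% | 2.6% |
| Subset N=40, null 5% | 4.8–5.4% | 1.6–1.8% |

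Subset sizes and null rates are assumptions; the documents give neither. Further runs with six stratum mixes and 400,000 to 1,000,000 trials per scenario gave 6.1–6.6% v 4.8–5.1% at an 11–13% null.

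About half of the 1.2–1.6 point excess at 11–13% is therefore the unpooled variance itself (0.7–0.8 points unstratified). The rest comes from splitting 100 subjects into small cells. In the benefit direction the printed test rejects in 3.1–3.3% of null trials, against a nominal 2.5%.

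**At the planning effects.** Study-S power is 99.0–99.3% (printed) v 98.7–99.0% (CMH); Study-G is above 99.9% with both. The nominal 95% CI covers 93.2–93.6%.

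**The case against.** The strongest reply is that the formula is fully pre-specified. Every term is printed, the p-value is called approximate, and nobody could choose between tests after seeing the data. That is true of SAP 9.1, but it does not make a rule meet an alpha that it misses, and the protocol names a different test.

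Second, the primary endpoints are nearly untouched. This stands; the point should not be read as a threat to the primary conclusions.

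Third, the 7–10% figures need assumed subsets of 60 or 40 and null rates of 10–25%, and those endpoints are tested only if every earlier step succeeds. This stands: they are conditional figures. The 6.2–6.6% at N=100 does not depend on subset assumptions.

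Fourth, CMH is also off nominal in small, low-rate subsets, on the conservative side (1.6–3.5% at a 5% null, N=40–80). This stands as a cost.

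Fifth, SAP 14.0 attributes the specification of the categorical method to agency feedback. It does not say that this formula was requested, so the correspondence has to be read first.

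Finally, SAP 9.1's rules for empty cells must fit the new test. A stratum with an empty arm is not rare: with the 64/16/16/4 mix and blocks of 4 it occurs in about 12% of trials at N=100. The effect is small, because such a stratum adds zero to the CMH chi-square and carries very little weight in the estimate.

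**Conclusion.** The concern holds. SAP 9.1 labels an unpooled Wald test on the MH risk difference as a CMH test. At N=100 and a common response rate of 11–13%, its two-sided error is about 6.2–6.6%, against 4.8–5.0% for the test the protocol names. No stratum mix or allocation scheme tried brought it down to 5% at those rates. The excess is smaller at a 5% null rate and gone by about 3%, so low-rate endpoints such as complete clearance may be unaffected.

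This should be fixed, mainly for borderline results and for ranked binary secondaries with moderate placebo response. The MH risk difference itself is a sound estimate; the fault lies in the p-value and, to a lesser degree, the interval.

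**What to change.** First read the agency correspondence behind SAP version 2.0. If the agency did not ask for the printed formula, then before Period A unblinding:

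1. In SAP 9.1, for every binary comparison that relies on it (primary, ranked secondary, additional endpoints, tipping point), replace the p-value formula with: *The p-value is from the CMH chi-square (1 df, hypergeometric variance, no continuity correction), stratified by actual weight and number of prior biologic therapies.*
2. Keep the MH risk difference as the estimate. State that the 0.1 replacement applies to the estimate only, and that a stratum with an empty arm contributes nothing to the test.
3. Preferably replace the CI with a stratified Miettinen-Nurminen score interval using the same weights and a factor N_i/(N_i−1) in each stratum. At a difference of zero, with p = t/N and q = 1−p, its variance term is w²·p·q·(1/n+1/m)·N/(N−1) = n·m·t·(N−t)/[N²(N−1)], the CMH variance, so interval and p-value agree. Its coverage at the planning effects is 94.9–95.2%.
4. In SAP 9.3.3, leave the multiple-imputation pooling unchanged, but call it a pooled MH risk difference.

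If the agency did ask for the formula, keep it, name it a Wald test on the MH risk difference, and pre-specify the CMH chi-square as a sensitivity test. If unblinding has already happened, only report the CMH result alongside.

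The cost is SAP wording and a short root search for the interval. Primary power falls by about 0.3 points in Study-S and not noticeably in Study-G. Subset power falls more, partly because inflated error is removed: at an assumed 35% v 10%, from 82% to 78% (N=80), 71–72% to 65% (N=60) and 57–58% to 46% (N=40). If the Wald interval is kept beside the CMH p-value, the two can disagree in borderline cases.

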3.2 Secondary Endpoints

Ranked secondary endpoints are:

Study-G

1. Achievement of sPGA-G of 0 at Week 16, among subjects in the ITT_G population.
2. Achievement of DLQI of 0 or 1 at Week 16, among subjects in the ITT_G population.
3. Achievement of clinically meaningful (≥ 4 -point) improvement from baseline on the Genital Psoriasis Itch NRS at Week 16 among subjects with a baseline score ≥ 4 , among subjects in the ITT_G population.
4. Achievement of GenPs-SFQ item 2 score of 0 or 1 at Week 16 among subjects with a baseline score ≥ 2 , among subjects in the ITT_G population.

Study-S

1. Achievement of $\geq 90\%$ improvement from baseline in PSSI (PSSI 90) at Week 16, among subjects in the ITT_S population.

2. Achievement of PSSI 75 response at Week 16, among subjects in the ITT S population.
3. Change from baseline in PSS at Week 16, among subjects in the ITT S population.
4. Achievement of PSSI 100 response at Week 16, among subjects in the ITT S population.
5. Achievement of PSS of 0 at Week 16, among subjects in the ITT S population.

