9.2.2 Continuous Endpoints

Mixed-Effect Model Repeat Measurement (MMRM) will be the primary and only approach to handle missing data for continuous endpoints among all ITT Populations. The MMRM will be conducted using mixed model including observed measurements at all visits, using all available data even if a subject has missing data at some (but not all) post-baseline visits during the analysis period. An unstructured variance covariance matrix (UN) will be used. If the model cannot converge, an appropriate covariance structure matrix (e.g., autoregressive (1) or compound symmetry) will be used. The parameter estimations are based on the method of restrictive maximum likelihood (REML). The fixed effects will be used to report model-based means at corresponding visits.

Of note, during the Primary Analysis for Period A upon completion of Week 16, the MMRM analysis will only be performed at all visits up to Week 16.

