11.1.4 Psoriasis Symptoms Scale (PSS)

The PSS is a 4-item PRO instrument that assesses the severity of psoriasis symptoms in patients with moderate to severe psoriasis, using a recall period of 1 day. The symptoms include pain, redness, itching and burning from psoriasis. Current symptom severity is assessed using a 5-point Likert-type scale ranging from 0 (none) to 4 (very severe). Until Week 16, the weekly average score is calculated based on the 7 available daily scores from the days within each visit window that were closest to the nominal. If values from 4 or more days of the 7 day period are missing, then the rolling weekly average for that particular 7 day period will be set to missing.

The PSS was developed based on published evidence supporting the development of two similar, proprietary PRO instruments: the Psoriasis Symptom Inventory and the Psoriasis Symptom Diary.

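### The PSS MMRM has no baseline-by-visit term; adding one is a cheap safeguard for precision and conditional balance at Week 16

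*SAP*

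**What the plan says.** SAP 9.1 fits the MMRM "adjusting for the fixed effects of treatment, actual values of stratification factors at Baseline, Baseline value, visit and treatment by visit interaction as covariates". Protocol 7.4 gives the same terms: "The continuous endpoints will be analyzed using a MMRM, including baseline, adjusting for treatment, actual values of stratification factors, visit, and treatment by visit interaction". No other section of either document adds a baseline-by-visit interaction.

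Three further statements fix how the model works at Week 16:

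- SAP 9.2.2 on the residual covariance: "An unstructured variance covariance matrix (UN) will be used".
- SAP 9.2.2 on the primary analysis: "the MMRM analysis will only be performed at all visits up to Week 16". The activity schedule (Protocol Appendix D) has two post-baseline visits up to then, Week 4 and Week 16.
- SAP 3.2 on the third ranked secondary endpoint of Study-S: "Change from baseline in PSS at Week 16, among subjects in the ITT S population".

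SAP 11.1.4 describes PSS as four items scored 0 to 4, and until Week 16 "the weekly average score is calculated based on the 7 available daily scores". SAP 9.4.3 plans no sensitivity analysis for ranked secondary endpoints.

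**The concern.** The treatment effect may differ by visit in this model, but the baseline effect may not. The fitted slope is a compromise between Week 4 and Week 16, while the ranked endpoint uses Week 16 alone.

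The two slopes could well differ. Correlation with baseline tends to fade over time. PSS also cannot fall below 0, so as subjects clear, their change approaches minus their baseline. Both features steepen the slope of change on baseline by Week 16. A compromise slope would then under-adjust at Week 16. The variance would be somewhat larger than necessary. An arm that by chance starts with higher PSS would also keep part of that head start in its estimated change.

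PSS change is alpha-controlled and stands ahead of PSSI 100 and PSS of 0 in the Study-S hierarchy. It is the only continuous endpoint in either hierarchy.

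**Working it through.** **The plan's own figure.** The only power statement for Study-S concerns scalp IGA 0/1: placebo 11%, difference 37% (so risankizumab 48%), 50 per arm, two-sided 0.05, more than 90% power (SAP 2.4). A two-proportion calculation gives 98.9%, which agrees. No figure is given for PSS, so the inputs below are assumptions.

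**Formula.** Let b be the vector of visit-specific baseline slopes, R the residual covariance given baseline, and s0 the baseline SD. With two visits, unstructured covariance and complete data, the large-sample results are:

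- common slope: b_c = (1'R⁻¹b) / (1'R⁻¹1)
- Week 16 variance ratio, common against visit-specific slope: 1 + s0²(b16 − b_c)² / R16
- shift of the Week 16 estimate: (b16 − b_c) × baseline imbalance

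Using slopes of the score or of its change makes no difference, because subtracting baseline lowers every slope by 1.

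**Example 1, standardized.** Assume SD 1 throughout, correlation with baseline 0.7 at Week 4 and 0.4 at Week 16, and 0.5 between visits.

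- R4 = 1 − 0.49 = 0.51; R16 = 1 − 0.16 = 0.84; covariance = 0.5 − 0.28 = 0.22.
- Weights are proportional to 0.84 − 0.22 = 0.62 and 0.51 − 0.22 = 0.29.
- b_c = (0.62×0.7 + 0.29×0.4) / 0.91 = 0.604, so b16 − b_c = −0.204.
- Variance ratio = 1 + 0.0418/0.84 = 1.050; SE ratio 1.025.

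**Example 2, PSS-like.** Assume a 0–16 sum score, baseline SD 3.3, and slopes of change on baseline of −0.21 (placebo) and −0.48 (risankizumab) at Week 4, and −0.37 and −0.89 at Week 16.

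- Averaged over arms: −0.345 and −0.63.
- With equal residual SDs of 2.5, b_c is the midpoint, −0.4875, and b16 − b_c = −0.1425.
- Variance ratio = 1 + 10.89×0.0203/6.25 = 1.035.
- Over residual SDs of 2 to 3 and residual correlations of 0.4 to 0.7, the ratio runs from 1.00 to 1.11.

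**Range from the formula (SD 1 at every visit).**

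| Correlation with baseline, Week 4 / Week 16 (between visits) | SE ratio | Variance ratio | Shift per 1-SE baseline imbalance, in SEs |
|---|---|---|---|
| 0.5 / 0.5 (0.5) | 1.000 | 1.000 | 0 |
| 0.6 / 0.4 (0.5) | 1.009 | 1.017 | 0.13 |
| 0.7 / 0.4 (0.5) | 1.025 | 1.050 | 0.22 |
| 0.7 / 0.3 (0.5) | 1.047 | 1.096 | 0.31 |
| 0.8 / 0.2 (0.4), extreme | 1.129 | 1.276 | 0.52 |

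Over 36 combinations, with the SDs also varied, the SE ratio ran from 1.00 to 1.16.

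**Simulation, PSS-like scores, 50 per arm.**

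- Slopes of Example 2, 3,000 trials per scenario: variance ratio 1.067 with complete data and 1.051 with about 10% missing at random. The estimate moved −0.21 and −0.18 points per 1-point imbalance, against −0.02 and +0.02 with the interaction.
- Baseline mean 8, SD 3.3, scores floored at 0, complete data: variance ratios 1.03 to 1.07 and shifts −0.12 to −0.17 when slopes differed by visit. When slopes were equal or nearly so the ratio was 0.995 to 0.996, so the extra term cost essentially nothing.

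**Scale of the shift.** The SE of the baseline difference is 3.3×√(2/50) = 0.66 points. A 1-SE imbalance therefore moves the estimate by about 0.07 to 0.13 points at −0.1 to −0.2 per point. The SE of the Week 16 difference in the first simulation was 0.522.

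**Error rates under no effect (4,000 trials per scenario).** Overall rejection with the common slope was 4.8% to 5.7%. In the 4–5% of trials with an imbalance above 0.4 SD, rejection with unequal slopes was about 10–16%, against 4–7% with the interaction. Those cells hold only about 170 to 190 trials each.

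**Power.** The first simulation had a mean effect of −4.59, with SD 0.522 (common slope) or 0.505 (interaction). The z values are 4.59/0.522 = 8.8 and 4.59/0.505 = 9.1, and simulated power was 100% with either model. Only with the effect cut to about one third did power separate: 80% against 83% with complete data.

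**The case against.** The strongest case for leaving the model alone is that it is prespecified and identical in both documents. The SAP version history also lists an MMRM clarification in 9.1 among the changes made after agency feedback. Baseline is already a covariate, and the loss exists only if the slopes differ, on which the documents give no data. All of this stands. It shows that the plan is consistent and acceptable, but not that the common slope is preferable, and the version history does not say that this term was considered.

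It is also fair to say that the floor effect mainly makes slopes differ by arm (0.89 − 0.37 = 0.52 at Week 16 in Example 2) more than by visit (0.63 − 0.345 = 0.285). A baseline-by-visit term addresses only the second.

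A reader might infer three stronger points, which the material does not support:

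- **That the Week 16 test is biased or invalid.** Randomization keeps the estimate unbiased over all trials, and overall type I error was near nominal. The excess rejection is conditional on a large imbalance.
- **That the misfit damages the handling of missing values**, because SAP 9.2.2 says "Mixed-Effect Model Repeat Measurement (MMRM) will be the primary and only approach to handle missing data for continuous endpoints among all ITT Populations". With about 9% missing at random, both models averaged −4.635 against a true −4.59, so the extra term changed nothing.
- **That PSSI 100 and PSS of 0 are at risk of not being tested.** At the assumed effect, power for PSS change is 100% either way.

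**Conclusion.** The point holds as a low-cost improvement in efficiency and conditional balance. It is not an error in the plan. If the baseline slope differs between Week 4 and Week 16, the Week 16 variance for PSS change is about 1.00 to 1.07 times what it need be under moderate assumptions. At 1.07, 100 subjects carry the information of about 93 (100/1.07). Steeper fading of the correlation with baseline gives larger ratios. The estimate keeps about −0.1 to −0.2 points per 1-point chance imbalance, in the direction that flatters whichever arm starts higher. With equal slopes both effects vanish.

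These sizes rest on assumed PSS variances, slopes and correlations, and on a 0–16 sum score that SAP 11.1.4 does not spell out. The direction of the result does not depend on those choices, but its size does.

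**What to change.** Add a baseline value by visit interaction to the MMRM fixed effects in SAP 9.1, for PSS and for the other continuous endpoints that use the same model. List it in SAP 14.1 as a refinement of Protocol 7.4. If the sponsor prefers the common slope, one sentence of justification in SAP 9.1 would do. The change should be in place before the Week 16 data are unblinded.

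The cost is one extra parameter in the two-visit Period A model and four in a model with all five post-baseline visits. It needs no new data and leaves the estimand and the testing order unchanged.
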